### 8.5 Risk-to-Benefit Rationale

In summary, the risks involved with the investigational devices to be evaluated under this umbrella investigation are not substantially different from the risks associated with normal CI users, and the risks involved with the clinical investigation procedures are not substantially different from the risks associated with a normal clinical session for CI users.

The potential temporary inconveniences and discomforts associated with participation in one or more sub-studies under this umbrella investigation is proportional to the potential direct short-term benefits possible increased hearing performance, or indirect benefits, as described in section 8.1.

## **9 STATISTICAL CONSIDERATIONS**

### 9.1 General Considerations

Data will be analysed separately per sub-study. Analysis of the data will take place at Cochlear. Substudy specific endpoints and other statistical considerations such as hypothesis and sample size

determination will be described in the sub-study documentation and a sub-study CIR will be written when these endpoints are reached.

Clinical Investigation Plan |

Approval Date (GMT+

### 9.2 Endpoints

Each sub-study addresses aspects of one or more of the innovations described in section 4.1. Substudy specific endpoints and details such as specific measurements and time points for assessment of each measure, will be described in the sub-study documentation.

### 9.2.1 Primary Endpoint

Monosyllabic word in quiet scores (for standard-of-care and new/optimized device fitting methods).

### 9.2.2 Secondary Endpoints

There are no secondary endpoints stated in the umbrella investigation, however, will be specified in the sub-study documentation if appropriate.

#### 9.2.3 Exploratory Endpoints

There are no exploratory endpoints stated in the umbrella investigation, however, they will be specified in the sub-study documentation if appropriate.

### 9.3 Hypotheses

Sub-study specific hypotheses and details such as margins for the hypothesis's tests, will be described in the sub-study documentation.

#### 9.3.1 Primary Hypothesis

There are no primary hypotheses stated in the umbrella investigation, however, they will be specified in the sub-study documentation.

#### 9.3.2 Secondary Hypotheses

There are no secondary hypotheses stated in the umbrella investigation, however, they will be specified in the sub-study documentation if appropriate.

#### 9.3.3 Exploratory Hypotheses

There are no exploratory hypotheses stated in the umbrella investigation, however, they will be specified in the sub-study documentation if appropriate.

### 9.4 Sample Size Determination

This umbrella study explores the feasibility phase of new or improved fitting, diagnostic and (re)habilitation software, research fitting and research diagnostic tools.

Sample size requirements will be described in the sub-study documentation. A maximum of 160 subjects will be recruited to participate in sub-studies under this umbrella investigation.

## 9.5 Analysis Populations

A detailed description of the statistical analysis that will be used for each sub-study will be described in the sub-study documentation.

## 9.6 Primary Endpoint Analyses

Primary endpoint analysis will be done on the level of the sub-study. A detailed description of the statistical analysis will be specified in the sub-study documentation.

## 9.7 Secondary Endpoint Analyses

There are no secondary endpoints stated in the umbrella investigation, however, they will be specified together with a detailed description of the statistical analysis in the sub-study documentation if appropriate.

## 9.8 Exploratory Endpoint Analyses

There are no exploratory endpoints stated in the umbrella investigation, however, will be specified together with a detailed description of the statistical analysis in the sub-study documentation if appropriate.

## 9.9 Safety Analyses

Per sub-study adverse events will be listed by verbatim term, according to severity, seriousness and relationship to the investigational device and investigation procedures. Also, device deficiencies will be listed by verbatim term.

### 9.10 Interim Analyses

Not applicable, unless specified differently in sub-study documentation.

## **10 INFORMED CONSENT PROCESS**

The Investigator shall obtain written informed consent from the subject using an approved ICF prior to any clinical investigation-related examination or activity. The rationale of the clinical investigation, as well as the risks and benefits, what participation will involve, and alternatives to participation will be explained to the subject. Ample time will be provided for the subject to enquire about details of the clinical investigation and to decide whether to participate.

All questions about the clinical investigation shall be answered to the satisfaction of the subject or the subject's legally acceptable representative. Subjects shall not be coerced or unduly influenced to participate or to continue to participate in a clinical investigation.

Each subject (or their legally authorised representative) and the person who conducted the informed consent discussion, shall sign and date the ICF. Where required, a witness shall sign and personally date the ICF. A copy of the signed ICF shall be given to the subject. The original signed ICF shall be archived in the Investigator's Site File or subject file at the investigational site.

The subject, or the subject's legally authorised representative, shall be informed in a timely manner if new information becomes available that may be relevant to the subject's willingness to continue

participation in the clinical investigation. The communication of this information must be documented as an update to the ICF and re-consent of the subject.

Clinical Investigation Plan |

Approval Date (GMT+

The external principal investigator or study staff of external principal investigator shall be responsible for subject recruitment and obtaining Informed Consent for the umbrella investigation AI5763. Each sub-study will have its own sub-study specific ICF in which the detailed procedure of the sub-study is described. All other aspects such as insurance and privacy verbatim of the ICF of umbrella study AI5763 still apply.

The principal investigator or study staff responsible for the conduct of the sub-study will obtain Informed Consent for each sub-study. The sponsor principal investigator of CTC/Cochlear, Melbourne will always receive a copy of the signed Informed Consent Form of AI5763 and the sub-study.

## **11 ADVERSE EVENTS AND DEVICE DEFICIENCIES**

## 11.1 Definitions

### 11.1.1 Adverse Event

An adverse event (AE) is any untoward medical occurrence, unintended disease or injury, or untoward clinical signs (including abnormal laboratory findings) in subjects, users or other persons whether or not related to the medical device or the procedures required for implant or use.

NOTE 1: This definition includes events related to the medical device or the comparator device.

NOTE 2: This definition includes events related to the procedures involved.

NOTE 3: For users and other persons, this definition is restricted to events related to medical devices.

#### 11.1.2 Adverse Device Effect

An adverse device effect (ADE) is an AE related to the use of a medical device.

NOTE 1: This includes any AE resulting from insufficiencies or inadequacies in the instructions for use, the deployment, the implantation, the installation, the operation, or any malfunction of the medical device.

NOTE 2: This definition includes any event resulting from use error or from intentional misuse of the medical device.

#### 11.1.3 Serious Adverse Event

A serious adverse event (SAE) is any AE that:

- 1) led to a death,
- 2) led to a serious deterioration in the health of the subject that either resulted in:
- a life-threatening illness or injury, or
- a permanent impairment of, or damage to, a body structure or a body function, or
- in-patient hospitalisation or prolonged hospitalisation, or

• medical or surgical intervention to prevent life-threatening illness or injury or permanent impairment or damage to a body structure or a body function, or

Clinical Investigation Plan |

Approval Date (GMT+

- Chronic disease.
- 3) led to foetal distress, foetal death or a congenital physical or mental abnormality, or birth defect

NOTE: Planned hospitalisation for a pre-existing condition, or a procedure required by the CIP, without serious deterioration in health, is not considered a SAE.

#### 11.1.4 Serious Adverse Device Effect

A serious adverse device effect (SADE) is an ADE that has resulted in any of the consequences characteristic of a SAE.

#### 11.1.5 Unanticipated Serious Adverse Device Effect

An unanticipated serious adverse device effect (USADE) is a SADE, which by its nature, incidence, severity, or outcome has not been identified in the current version of the Investigator's Brochure or CIP.

NOTE: An anticipated serious adverse device effect is an effect, which by its nature, incidence, severity, or outcome has been identified in the the current version of the Investigator's Brochure or CIP.

#### **11.1.6 Adverse Events of Special Interest**

There are no Adverse Events of Special Interest.

#### 11.1.7 Device Deficiency

A Device Deficiency (DD) is an inadequacy of a medical device with respect to its identity, quality, durability, reliability, safety, or performance.

NOTE: Device Deficiencies include malfunctions, use errors, and inadequate labelling or information supplied by the manufacturer.

### **11.2 Recording and Handling of Adverse Events**

Subjects shall be carefully monitored during the clinical investigation of the sub-study and the investigator should enquire about AEs at investigation visits.

All AEs will generally be recorded on sub-study basis from the time of treatment assignment and continue for each subject until completion of their End of Study visit. Where the involves acute treatment only, AE will be recorded only from the time of treatment assignment and continue for each subject until 4 hours after their study visit. Ongoing SAEs and SADEs will be followed for 30 days, or until resolution or stabilisation of the event, whichever comes first. Any variations to these requirements will be documented in each sub-study documentation (for example, variations to account for in-booth only or take-home use).

Source notes should indicate the evaluation for AEs, even if there was none to report. All required AEs will be reported if observed, even if anticipated and/or acknowledged as a risk factor in the consent.

All AEs will have the following information documented: start and stop dates, action taken, outcome, severity and investigators opinion on the potential relationship to the IMD and/or comparator and study procedures. If an AE changes in severity, the most severe (highest) grade will be captured for that event on the Adverse Events CRF.

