## 7 DESIGN OF THE CLINICAL INVESTIGATION

## 7.1 General

This is a feasibility, prospective, with sequential enrolment, multicenter, clinical investigation in adults and paediatrics with a CE approved Nucleus cochlear implant.

Subjects older than 10 months will be included. Subjects will be screened and up to 160 eligible subjects will be recruited in the umbrella investigation.

Two separate groups of subjects will be recruited:

- Group 1 will include subjects who are already implanted with a Nucleus cochlear implant. A clinical setting can consist of therapeutic elements (fitting, diagnostic or rehabilitation) and evaluations. Subjects will be assessed with the commercially available Nucleus sound processor. Acute testing will be done where possible. Take home use will be applied when learning effects may play a significant role and to evaluate the acceptance of the different fitting, diagnostic and (re)habilitation methods in as many listening environments as possible. The subject might be asked to complete questionnaires, to perform at-home tests etc. during this take home use and/or at the clinical visits. The time for a clinical visit will be limited to a maximum of 4 hours. The time in between clinical visits will vary with typical spacing of between 0 (acute) to 4 weeks.
- Group 2 will include subjects who are scheduled to be implanted with a commercially available Nucleus cochlear implant. The diagnostic testing will be conducted in the operating theatre during the cochlear implant surgery. Only CE approved devices will be used for this intraoperative testing in accordance with the approved indication(s) and terms of the market authorization. Post-operatively, these subjects might be recruited following the procedures as described for the group 1 subjects.

Figure 5 illustrates the subject enrolment scenarios for group 1 and group 2 subjects.

Subjects will attend scheduled study visits over a period up to 5 years in different sub-studies as described in the sub-study documentation.

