A clinical setting can consist of therapeutic elements and evaluations. Subjects will be assessed with the commercially available Nucleus sound processor if required. Acute testing will be done where possible. Take home use will be applied when learning effects may play a significant role and to evaluate the acceptance of the new listening program, diagnostic or rehabilitation tool in as many listening environments and/or in daily life as possible. The subject might also be asked to complete questionnaires, to perform at-home tests etc. during this take home use and/or at the clinical visits. The time for a clinical visit will be limited to a maximum of 4 hours. The time in between clinical visits will vary with typical spacing of between 0 (acute) to 4 weeks.

The description of the measures taken to minimize bias, such as randomization and blinding, will be described in each sub-study specific documentation. Also, the sub-study specific method and timing for assessing, recording and analyzing variables, the equipment used, the monitoring maintenance and calibration will be described in the sub-study specific documentation.

Section 7.3 describes the procedure used in the umbrella investigation.

Safety will be assessed by recording and summarizing all Adverse events (AEs)/Adverse Device Effects (ADEs) and Device Deficiencies (DDs). Sub-study specific endpoints and details such as specific measurements and time points for assessment of each measure, will be described in each sub-study specific study documentation. No Independent Data Monitoring Committee (IDMC) will be used for this clinical investigation. Analyses, including interim analyses where required, will be specified in the sub-study CIP. All subjects will have an End-of-Study visit at the time they complete each sub-study and the umbrella study.

The specific study design of each sub-study will be described in the study documentation of the substudy.

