#### Intra-operative stage to collect objective measurements:

Only CE approved devices will be used for this intra-operative testing in accordance with the approved indication(s) and terms of the market authorization.

The investigator may request a nurse, the surgeon or a clinician to run the test under the investigator's supervision.

Video recording may be done during the testing where required.

If the intra-operative tests take significantly more time under anaesthesia (as judged by the surgeon) the testing will be aborted.

Post-operatively, these subjects might be recruited following the procedures as described for the group 1 subjects.

Where possible the comparing measurements will be provided blinded to subject and/or tester.

Subjects can participate in several sub-studies (one at a time).

The results of the tests will be carefully monitored during the study and compared with the baseline results and with the benchmark results (where applicable) typical for each category of subjects.

A detailed description of the procedure shall be provided in the sub-study specific documentation.

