### 7.4 Safety Evaluations and Procedures

The risks and anticipated ADEs for the investigational device, as identified in Sections 8.2 and 8.3 of the CIP, will be assessed in the clinical investigation via reporting of all AEs/ADEs from the time of first subject first visit until last subject last visit for every sub-study.

Safety data adjudication may be conducted by the Sponsor's Medical Officer in accordance with the Sponsor's standard operating procedures.

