**Non-auditory stimulation**: In rare cases, stimulation of the CI can lead to stimulation of non-auditory structures such as the facial nerve. It is a standard hazard in clinical management of hearing implant users. It is essentially controlled during fitting of the implant. Also, this will always be known already from the clinical experience with the subject and can be prevented by e.g. stimulating just below the level when the non-auditory stimulation occurs or by deactivating that specific electrode. Also, the fitting is conducted or overseen by an experienced clinician. The associated risk is not exceeding the normal clinical handling of a CI.

**Wrong stimulation delivered (within safety limits):** It is conceivable that due to an implementation error in research firmware or software a wrong stimulus would be delivered. Through thorough formal verification the probability that unintended electrical pulses would be delivered is low.

**Sub-optimal fitting of the device resulting in sub-optimal performance:** It is possible that investigational alternatives result in a decline of hearing outcomes. It is well known that some types of changes to a map may lead to an acute minor decline in hearing outcomes. As the CI user adapts to the new sound quality, this decline is often temporary. But in the worst case a user may not adapt, and he/she may decide not to wear the sound processor anymore, resulting in an absence of hearing. In this study a CI clinician will be available to provide hearing care, and address reports of degraded performance. Subjects will also have access to their standard baseline map that they can return to at all times. Again, this risk is similar to the risk in normal clinical management.

In the case of prolonged observed systematic decrease in performance the particular test setup/condition can be halted. Subjects can always revert to their baseline map as this is kept available to them. After the study has been finished, the patients will return to their original/preferred strategy/condition.

**Intra-operative testing only:** There is a risk that the intra-operative tests take longer and lengthen the time the subject is under anaesthesia. In this case the surgeon or anaesthetist can abort the testing.

In summary, the risks involved with the investigational devices are not substantially different from the risks associated with normal CI users and the normal clinical handling of a CI.

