#### 11.4.2 Sponsor Notification of Events

The Sponsor is responsible for reviewing all safety data to evaluate potential causality and anticipation of all ADEs.

The Sponsor is also responsible for reporting all reportable events according to the requirements and timelines of the regulatory authorities relevant to this clinical investigation, and shall conduct an expedited assessment of all SAEs, unanticipated ADEs, DDs that could have led to a SADE.

CTC: The sponsor is responsible for reporting to the FAMHP (Federal Agency for Medicines and Health Products): [contact], by using the MDCG 2020-10/2 form: (a) any serious adverse event that has a causal relationship with the investigational device, the comparator or the investigation procedure or where such causal relationship is reasonably possible; (b) any device deficiency that might have led to a serious adverse event if appropriate action had not been taken, intervention had not occurred, or circumstances had been less fortunate; and (c) any new findings in relation to any event referred to in points (a) and (b).

Reporting must be: a) for all reportable events which indicate an imminent risk of death, serious injury, or serious illness and that requires prompt remedial action for other patients/subjects, users or other persons or a new finding to it: immediately, but not later than 2 calendar days after awareness by sponsor of a new reportable event or of new information in relation with an already reported event; or b) any other reportable events or a new finding/update to it: immediately, but not later than 7 calendar days following the date of awareness by the sponsor of the new reportable event or of new information in relation of an SAE/SADE would be incomplete, on receipt of additional information the Sponsor must submit a clearly referenced and numbered follow-up report of the event.

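### The 4-hour limit on adverse event recording in 11.2 has no exception for Group 2 intra-operative testing, although 8.2 names longer anaesthesia as a risk of that testing

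*Combined protocol and SAP*

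**What the plan says.** Group 2 consists of people about to receive a commercial implant. Section 7.1 says of them: "The diagnostic testing will be conducted in the operating theatre during the cochlear implant surgery". Only CE approved devices are used, within their indication. Later participation is optional: "Post-operatively, these subjects might be recruited following the procedures as described for the group 1 subjects" (7.3, intra-operative stage).

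Section 8.2 lists one risk for this testing alone: "There is a risk that the intra-operative tests take longer and lengthen the time the subject is under anaesthesia". The stated control is that the surgeon or anaesthetist can stop the test. Section 8.3, in contrast, says that taking part carries no identified potential for physical or psychological harm.

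Section 7.4 says that the risks in 8.2 and 8.3 are assessed "via reporting of all AEs/ADEs from the time of first subject first visit until last subject last visit for every sub-study".

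Section 11.2 sets the window for each subject:

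- **General rule:** from treatment assignment to the End of Study visit. On the timing of that visit, 7.1 says: "All subjects will have an End-of-Study visit at the time they complete each sub-study and the umbrella study".
- **Only acute treatment involved:** "AE will be recorded only from the time of treatment assignment and continue for each subject until 4 hours after their study visit".
- **Serious events still ongoing:** followed for 30 days, or until resolved or stable if that is sooner.
- **Variations:** sub-study documents may change these rules. The examples given are in-booth and take-home use.

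**The concern.** The plan names a physical risk for one group and makes AE reporting the means of assessing it. It then sets a default window for acute work that may be too short to see that risk. Ill effects of longer anaesthesia can appear during recovery, and recovery can outlast 4 hours.

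An event that is never recorded cannot be assessed for causality or appear in the sub-study listing under 9.9. Nor can it reach the sponsor, who under 11.4.2 must report to the Belgian authority "any serious adverse event that has a causal relationship with the investigational device, the comparator or the investigation procedure". A sub-study report could then show nothing for this risk only because recording had stopped. Children older than 10 months may be in Group 2 in Belgium, where a sub-study strictly requires it (7.2.1 and 7.2.3).

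**Working it through.** There is no figure to recompute. The 4 hours is a stated rule, so the check is to set the provisions side by side and ask what happens to an event according to when it starts.

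**Step 1: which window applies to a theatre session?** The plan does not say. In the copy reviewed, the acute rule lacks the noun that would define its scope; I read it as the sub-study. A Group 2 sub-study limited to one session in theatre, with no take-home use, can reasonably be taken as acute only. That is an inference. If it is wrong, the general rule applies.

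**Step 2: what is captured under each rule?**

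| Onset of the AE | Acute-only rule applied | General rule applied |
|---|---|---|
| During the test or within 4 hours after the session | Recorded | Recorded |
| More than 4 hours after the session, before discharge | Not recorded | Recorded if the End of Study visit comes after onset; its timing relative to discharge is not fixed |

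**Step 3: what if an early event becomes serious later?** Section 11.1.3 makes "in-patient hospitalisation or prolonged hospitalisation" a possible result of an AE. The AE itself is the untoward occurrence that leads to it. If a complication starts within 4 hours and later delays discharge, its onset is inside the window. Section 11.4.1 requires AEs that meet the serious criteria to be reported without delay, and the forms to be updated as information arrives. Such events are covered.

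**Step 4: do other provisions cover the later events?**

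- The 30-day clause follows serious events that are ongoing. It does not extend first recording to an event that starts after the window has closed.
- The option to vary the window could cover them. But neither example is about theatre, so nothing prompts the author of an intra-operative sub-study to use it.
- The abort rule limits exposure but does not detect harm. The umbrella plan also does not ask for test duration or aborts to be recorded, so added time under anaesthesia is not measured directly.

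The exposed set is therefore AEs that start more than 4 hours after the session, in sub-studies that follow the acute default.

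**The case against.** The strongest objection is that the acute rule was not written for theatre. Elsewhere the plan uses the word acute for laboratory or clinic sessions (4.3, 7.3, and the Group 1 text in 7.1). The Group 2 and intra-operative text never uses it. The version 6.0 entry in section 25 adds the acute AE rule alongside a change in clinic visit spacing. This stands as a reason for caution: the plan does not place Group 2 under the 4-hour rule. Equally, it does not exclude Group 2.

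Second, each sub-study has its own plan, which may set a longer window. Those plans are not available here, so the point concerns the umbrella default only.

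Third, the added exposure is limited. Implantation happens independently of the study, the tests are in common intra-operative use, and testing is stopped if it takes significantly longer. This lowers the stakes but does not supply a recording window.

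A reader might also infer three stronger points that the documents do not support:

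- **That 7.4 and 11.2 contradict each other.** Section 7.4 gives a period for the whole sub-study and 11.2 a window for each subject. The two can coexist.
- **That the general rule would also stop on the day of surgery.** Nothing places the End of Study visit there. Investigators are to ask about AEs at visits, which cannot be done under anaesthesia, so a visit after recovery is plausible.
- **That prolonged hospitalisation recognised late would be lost.** Late recognition is not late onset, as step 3 shows.

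**Conclusion.** The gap in the umbrella default is real but conditional. If a sub-study treats intra-operative testing as acute only and follows 11.2 unchanged, post-anaesthetic AEs with onset more than 4 hours after the session are not recorded. Yet AE reporting is how 7.4 says the anaesthesia risk will be assessed. It does not follow that Group 2 events have been or will be missed.

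The size cannot be stated in events or subjects. The maximum of 160 is not divided between the groups, and the documents give no time to discharge and no rate of post-anaesthetic events.

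The conclusion rests on two assumptions: that a single theatre session is read as acute treatment, and that the sub-study plan does not set its own window. It is worth correcting at the next amendment, because a stated default would otherwise govern a situation it does not address.

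**What to change.** Add to 11.2: *The 4-hour limit does not apply to intra-operative testing. For Group 2, SAEs and any AE judged possibly related to the intra-operative test or to prolonged anaesthesia are recorded from the start of the test until hospital discharge, from hospital notes.*

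Have intra-operative sub-studies record the test start time, stop time and any abort, so that the time the test takes under anaesthesia is measured. Qualify the statement in 8.3 that no harms were identified, so that it refers to the anaesthesia risk in 8.2.

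Limiting the non-serious events to those possibly related keeps routine events of implant surgery out of the CRF. Recording every AE to discharge would require severity, causality, action and outcome for each of them. The documents give no basis for a particular window length. Discharge is proposed because a delayed discharge can be judged by then and the check needs no study visit.

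The cost is a few CRF items and one check of the notes per Group 2 subject, plus a CIP amendment under section 18. Section 16 requires written ethics committee approval if the amendment is substantial. Section 10 requires an updated consent form and re-consent if the change is treated as relevant new information for subjects. Where a sub-study already sets a longer window, the edit only corrects the default.
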